## **NUMBER OF PARTICIPANTS**

### **Part 1:**

Sixteen participants will be enrolled in order to obtain at least 12 evaluable participants.

### **Part 2:**

A maximum of 8 participants will be enrolled to assess the taste masking of RO7017773.

## **CONCOMITANT MEDICATIONS**

### **Permitted Therapy**

Use of the following therapies is permitted, as specified below:

- Continuation of hormone-replacement therapy is permitted throughout the study for participants who already use them.
- Acetaminophen/paracetamol is allowed up to a maximum dose of 2 g/day up to 48 hours prior to dosing and after the in-house period, but should not exceed 4 g total during the week prior to dosing.

### **Prohibited Therapy**

As a general rule, no concomitant medication will be permitted, with the exception of medications to treat AEs and medications listed permitted medication, unless the rationale for exception is discussed and clearly documented between the Investigator and the Sponsor.

Use of the following therapies is prohibited during the study and for at least 30 days or at least 5 half-lives prior to initiation of study treatment, unless otherwise specified below:

- Any prescribed or over-the-counter medication (including herbal products, vitamin, mineral, energy drinks and dietary supplements), unless specified in [Section 6.5.1](#).
- Any known inhibitor of CYP3A4 or P-glycoprotein taken within 4 weeks prior to start of administration of study drug (Day 1) or within 5 times the elimination half-life of the medication prior to start of study drug intake (whichever is longer) including but not limited to the following drugs: ketoconazole, itraconazole, fluconazole, erythromycin, clarithromycin, nefazodone, diltiazem and verapamil.
- Any known inducer of CYP3A4 or P-glycoprotein taken within 2 weeks prior to start of administration of study drug (Day 1), including but not limited to the following drugs: rifampicin, rifabutin, glucocorticoids, carbamazepine, oxcarbazepine, phenytoin, phenobarbital, and St. John's Wort.

## 1.2 SCHEMATIC OF STUDY DESIGN

The study is designed in two parts. Part 1 is described in [Table 1](#) and [Table 2](#). Part 2 is described in [Table 3](#) and [Table 4](#).

**Table 1 Part 1 – 4 Period Crossover**

Screening	Periods Treatment A – D*	Follow-up
Day -28 to Day -2	
 
Randomization to treatment sequence prior to first period
 
Dosing on Day 1 with PK sampling up to Day 5
 
Total of 7-10 days between each period including washout
 
	7 to 14 days after last dose

\*Treatment A: Phase I capsule swallowed whole under fasted conditions

Treatment B: Phase II tablet swallowed whole under fasted conditions

Treatment C: Phase II tablet swallowed whole under fed conditions

Treatment D: Phase II tablet dispersed in water under fasted conditions including taste assessment

Prior to the first dosing, participants of Part 1 will be randomized to one of the four treatment sequences from a 4-period Williams Latin Square as defined in [Table 2](#).

**Table 2 Part 1 – Randomization to treatment sequences**

Treatment Sequence	Period 1	Period 2	Period 3	Period 4
1	A	B	C	D
2	B	D	A	C
3	C	A	D	B
4	D	C	B	A

**Table 3 Part 2 – 2 Period Crossover**

Screening	Periods Treatment A – B*	Follow-up
Day -28 to Day -2	
 
Randomization to treatment sequence prior to first Period
 
Dosing on Day 1 with PK sampling up to Day 5
 
Total of 7-10 days between each period including washout
 
	7 to 14 days after last dose

\*Treatment A: Phase II tablet containing flavor and/or sweetener dispersed in water under fasted conditions including taste assessment

Treatment B: Phase II tablet without flavor and/or sweetener dispersed in apple juice under fasted conditions including taste assessment

Prior to the first dosing, participants of Part 2 will be randomized to one of the two treatment sequences as defined in [Table 4](#).

**Table 4 Part 2 – Randomization to treatment sequences**

Treatment Sequence	Period 1	Period 2
1	A	B
2	B	A

For details of the dosing regimen in Part 1 and Part 2, see [Section 4.1.1](#)

### **1.3 SCHEDULE OF ACTIVITIES**

The schedule of the activities is provided in [Table 5](#).

**Table 5 Schedule of Activities for Part 1 and Part 2**

Day	Screening	Study Days in Each Period										Follow Up Visit k
		Day -1	Day 1					Day 2	Day 3	Day 4	Day 5	
Scheduled Time	Up to -28 days											
Informed Consent	X											
Demography	X											
Medical History	X											
Inclusion/exclusion criteria review	X	X										
Physical Examination a	X	X									X	X
In-house Period		X	X	X	X	X	X	X	X	X	X	
Ambulatory visit												X X X
Discharge from unit											X	
Vital Signs b	X	X	X							X	X	X
ECG-12 lead c	X	X	X		X	X	X	X	X	X	X	X
Serology	X											
Pregnancy Test d	X	X										X
Hormone Panel e	X											
Alcohol Breath Test	X	X										
Urine Cotinine Test	X	X										
Urine Drugs of abuse	X	X										
Urinalysis	X	X									X	X
Blood Chemistry	X	X									X	X
Hematology	X	X									X	X
Coagulation	X											
Randomization f			X									
Administration of Study Medication g				X								
Standard Meal h			X i				X		X	X	X	
Previous and Concomitant Treatments	X	X	X	X	X	X	X	X	X	X	X	X
Adverse Events	X	X	X	X	X	X	X	X	X	X	X	X

[figure not shown]
**Table 5 Schedule of Activities for Part 1 and Part 2 (cont.)**

- a) Physical examination will include body weight at screening and follow-up, and height at screening when BMI will be derived.
- b) Vital signs will include blood pressure, pulse rate and body temperature. Temperature will be recorded at screening, Day 1 predose and follow-up. All measurements will be taken after the subject has rested in a supine position for at least 5 min.
- c) Triplicate 12-lead ECGs will be collected after the subject has rested in a supine position for at least 10 min.
- d) Pregnancy test for females. Serum test at screening, urine test at Day -1.
- e) Hormonal panel for postmenopausal women only.
- f) Randomization only in Period 1 of each Part
- g) [REDACTED]
- h) [REDACTED]
- i) [REDACTED]
- j) [REDACTED]
- k) The follow up visit is 7 to 14 days after the last dosing.

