**Table 6 Objectives and Endpoints**

	Objectives	Endpoints
Primary		
PART 1	
 
• To assess the relative bioavailability of Phase II tablet formulation compared to Phase I capsule formulation of RO7017773 swallowed whole under fasting conditions following single oral dose administration.
 
	
 
• RO7017773 concentrations and RO7017773 pharmacokinetics (PK) parameters
 

PART 2	
 
• To assess the taste masking of RO7017773 Phase II tablet formulation containing sweetener and flavor dispersed in water and the RO7017773 Phase II tablet formulation without sweetener and flavor dispersed in apple juice.
 
	
 
• Taste questionnaire
 

Secondary		
PART 1	
 
• To assess the PK of RO7017773 Phase II tablet formulation dispersed in water or swallowed whole.
 
• To assess the effect of a high-fat meal on the PK (PK) of a single oral dose of RO7017773 Phase II tablet formulation.
 
• To assess the taste of RO7017773 Phase II tablet formulation without sweetener and flavor dispersed in water.
 
	
 
• RO7017773 concentrations and RO7017773 PK parameters
 
• RO7017773 concentrations and RO7017773 PK parameters
 
• Taste questionnaire
 

PART 2	
 
• To assess the PK of RO7017773 Phase II tablet formulation containing sweetener and flavor dispersed in water and the RO7017773 Phase II tablet formulation without sweetener and flavor dispersed in apple juice.
 
	
 
• RO7017773 concentrations and RO7017773 PK parameters
 

ALL PARTS	
 
• To evaluate the safety and tolerability of single oral doses of different RO7017773 formulations in healthy participants.
 
	
 
• Incidence and severity of AEs.
 
• Changes in vital signs, physical findings, ECG parameters, and clinical laboratory results during and following RO7017773 administration
 

Tertiary/Exploratory		

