#### **4.1.2 Length of the Study**

##### **Part 1- 4 Period Crossover**

The total duration of the study for each participant will be approximately 9 weeks divided as follows:

- Screening: Up to 4 weeks.
- In clinic periods: Day -1 to Day 3 for each of the 4 treatments.
- Treatment Periods: Day 1 to Day 5 for each of the 4 treatments (with single dosing on Day 1 of each period).
- Washout period 7 to 10 days (washout period is counted from Day 1 dose, i.e., overlapping with treatment period).
- Safety follow-up: 7 to 14 days after last dose.

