### **4.2 SCIENTIFIC RATIONALE FOR STUDY DESIGN**

The study rationale is provided in [Section 2.1](#).

A crossover design is used in each study part to reduce the residual variability as every subject acts as their own control. Subjects will be randomized to treatment sequences in each study part to minimize assignment bias. A washout of at least 7 days between RO7017773 doses is considered sufficient to prevent carryover effects of the treatments.

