### **8.2.2 Vital Signs**

Vital signs will include temperature (*oral or tympanic*), systolic and diastolic blood pressure and pulse rate. The vital signs will be measured in a supine position after at least 5 minutes rest at the time point specified in the SoA table ([Section 1.3](#)).

Blood pressure and pulse measurements will be assessed with a completely automated device. Manual techniques will be used only if an automated device is not available. When possible, the same arm should be used for all blood pressure measurements.

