### **8.10.2       Assessments during Treatment**

Under no circumstances will participants who enroll in this study and have completed treatment as specified, be permitted to re-enroll in the study. Participants may take part in only one part of the study.

All assessments must be performed as per SoA (see [Section 1.3](#)). Assessments scheduled on the day of study treatment administration should be performed prior to administration of study treatment, unless otherwise noted in the schedule of assessments.

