17.1.4 Vital Signs

Descriptive statistics summarizing vital signs by treatment and scheduled time will be provided.

All vital signs will be listed by subject.

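### No body temperature is scheduled within a treatment period after dosing, so the planned temperature summaries by treatment cannot show an on-drug effect

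*Protocol*

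**What the plan says.** The timing of temperature is fixed by one sentence in footnote b of protocol Table 5, carried word for word into SAP Appendix 2: "Temperature will be recorded at screening, Day 1 predose and follow-up".

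Other places treat temperature as a safety outcome:

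- Protocol 8.2.2: "Vital signs will include temperature (*oral or tympanic*), systolic and diastolic blood pressure and pulse rate".
- Protocol Table 6, secondary endpoint for all parts: "Changes in vital signs, physical findings, ECG parameters, and clinical laboratory results during and following RO7017773 administration".
- SAP 17.1 lists body temperature among the safety variables, and SAP 17.1.4 says: "Descriptive statistics summarizing vital signs by treatment and scheduled time will be provided".

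Three statements fix how long after a dose the next temperature falls:

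- Protocol 4.1.2 sets 7 to 10 days between doses, counted from the Day 1 dose.
- Table 5, footnote k: "The follow up visit is 7 to 14 days after the last dosing".
- Protocol 4.2: "A washout of at least 7 days between RO7017773 doses is considered sufficient to prevent carryover effects of the treatments".

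**The concern.** A safety endpoint defined as change during and after dosing needs at least one reading taken while the drug may be acting. For temperature, the schedule gives a screening value, a value before each dose and a value at follow-up. A table of temperature by treatment would look like on-treatment safety data. Its in-period entries, however, would all precede the treatment that labels the row.

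Such a table would look unremarkable whatever the drug did to temperature, and a reader of the study report could take it as reassurance.

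**Working it through.** No power, alpha or sample-size figure is involved. The check is a count of planned readings and of the time since the last dose.

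**Planned temperatures per participant** (footnote b; Table 5 applies its study-day columns to each period):

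- Part 1, four periods: 1 screening + 4 predose + 1 follow-up = 6.
- Part 2, two periods: 1 screening + 2 predose + 1 follow-up = 4.

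**Time from the most recent dose, for readings taken after at least one dose:**

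| Reading | Days since last dose | Source |
|---|---|---|
| Predose reading, Period 2 onwards | 7 to 10 | Protocol 4.1.2 |
| Follow-up | 7 to 14 | Table 5, footnote k |

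The earliest is 7 × 24 = 168 h. The period itself ends on Day 5, which is 4 × 24 = 96 h after a Day 1 dose. No planned temperature falls between dosing and 96 h, and none before 168 h.

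**Dosing periods affected:** 16 × 4 = 64 in Part 1 and at most 8 × 2 = 16 in Part 2, since 8 is a maximum. Planned in-period post-dose temperatures: 0 in each part.

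**Is the drug still relevant at 168 h?** No half-life is visible in the released documents. The statement that it is not rests on the protocol's own position in 4.2 that at least 7 days prevents carryover. If that position is right, the predose values in later periods and the follow-up value are effectively off-drug.

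**Does the analysis plan repair this?** It does not. SAP 9.2.1 sets the default baseline as the last value before the first study drug administration, so later predose values would be compared with an earlier predose value. SAP 9.1.6 lists unscheduled measurements but, apart from those used as baseline, keeps them out of the descriptive statistics.

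**Blood pressure, from the visible table.** Counting columns with screening as column 1, the protocol's Vital Signs row is marked in columns 1, 2, 3, 10, 11 and 12, and the ECG row in columns 1, 2, 3 and 5 to 12. Vital signs thus have no mark in columns 4 to 9. Columns 10 and 11 are post-dose marks within each period. Their day is uncertain: the header puts them at Day 4 and Day 5, but discharge is also in column 11 and protocol 4.1 ends the clinic stay on Day 3, which points to about Day 2 and Day 3.

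**The case against.** The strongest reply is that this is a deliberate and proportionate choice. The trial is a single-dose bioavailability and taste study, safety is secondary, protocol 9.1 plans no formal hypothesis tests, and the temperature timing is stated identically in both documents. No visible text names temperature as a risk for this compound. The earlier clinical results that might justify light monitoring are redacted or sit in the Investigator's Brochure. Adverse events are collected throughout, and unscheduled measurements can be taken and listed. All of this stands, and it limits the importance of the point. It does not give the endpoint any planned on-drug temperature.

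A reader might go further and infer that blood pressure on Day 1 is measured only before dosing, and that the trial therefore cannot detect a blood pressure change at peak exposure. The blank in columns 4 to 9 invites this, as does protocol 8.10.2: "Assessments scheduled on the day of study treatment administration should be performed prior to administration of study treatment". The documents do not support that conclusion:

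- The 8.10.2 sentence goes on to allow exceptions noted in the schedule. The row that would hold the clock times is blank, and footnotes g to j are redacted.
- The column alignment is unreliable. The header disagrees with the discharge day, and the study drug administration mark is in column 4 in the protocol but column 3 in the SAP copy.
- No time of peak concentration is visible, so peak exposure cannot be placed relative to any reading.
- Post-dose blood pressure is marked later in every period, and the post-dose ECGs supply heart rate.

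A comparison with the number of post-dose ECG columns on Day 1 is no firmer. It gives three (columns 5 to 7) if Day 1 is columns 3 to 7 as in the header, and five (columns 5 to 9) if Day 1 is columns 3 to 9.

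**Conclusion.** The point holds for temperature. It rests on the wording of footnote b and not on the layout of the table. No temperature is planned in any treatment period after dosing, and the first one after any dose is at least 7 days later. The summaries in SAP 17.1.4 therefore cannot show an on-drug temperature effect. This assumes that the footnote is followed as written and that the protocol's washout statement in 4.2 is sound.

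The effect on the trial is modest. One component of a descriptive secondary endpoint carries no on-treatment information. The bioavailability, food-effect and taste objectives are untouched, and a temperature change that produced symptoms could still be reported as an adverse event.

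For blood pressure, the documents support only a question to the sponsor.

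**What to change.** 1. In footnote b of Table 5, and in its copy in SAP Appendix 2, add temperature at the post-dose vital-sign time points already scheduled in each period.
2. In SAP 17.1.4, summarise post-dose temperature as change from the same period's predose value. SAP 9.2.1 allows a baseline other than the default if it is stated.
3. If the schedule is left as it is, state in the SAP and the study report that temperature is not an on-treatment safety measure and that its by-treatment summaries carry no information about drug effect.

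The cost is a minor amendment and a minute or so of staff time per time point. No extra visit, blood draw or participant is needed. The added readings would be in-period, but without a visible time of peak concentration they cannot be claimed to fall at peak.

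Separate query: the sponsor should check against the unredacted table whether any blood pressure reading is scheduled after dosing on Day 1. The answer should be reconciled with the endpoint in Table 6 and with the vital-signs criterion in protocol 4.1.3.

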## 2. **INTRODUCTION**

### 2.1 **STUDY RATIONALE**

RO7017773 is a selective gamma-aminobutyric acid type A (GABAA)  $\alpha 5$  subunit-containing receptor positive allosteric modulator. RO7017773 is being developed for the treatment of the two core domains of autism spectrum disorder (ASD); social communication deficits and repetitive behaviors. RO7017773 has the potential to normalize GABAergic signaling in key brain regions implicated in ASD without the side-effects of non-specific GABA modulators (e.g., benzodiazepines).

The rationale for the study design is provided in [Section 4.1.3](#).

### 2.2 **BACKGROUND**

ASD is a complex, heterogeneous neurodevelopmental disorder characterized by two core domains: impairments in social interaction and communication, and presence of repetitive or restricted behaviors, interests, or activities ([American Psychiatric Association 2013](#)). The Autism and Developmental Disabilities Monitoring Network recently reported that the estimated prevalence of ASD in the United States for the year 2010 was 14.7 per 1000 (1 in 68) children 8 years of age ([CDC 2014](#)).

No approved pharmacological treatment exists for the core social communication and social interaction deficits and repetitive behavior of ASD, and this disorder continues to be an area of high unmet medical need. Current treatments for associated symptoms of ASD may include antipsychotics (risperidone and aripiprazole) used for the treatment of irritability associated with ASD symptoms. Multiple lines of evidence suggest that an imbalance between excitatory/inhibitory neurotransmission in favor of excitation may arise from a dysfunction of the GABAergic signaling system (the main inhibitory neurotransmitter system in the brain) and plays a key role in these processes and contributes to the pathophysiology of ASD.

#### 2.2.1 **Background on RO7017773**

RO7017773 is a potent positive allosteric modulator (PAM) of the GABAA  $\alpha 5\beta 3\gamma 2$  receptor subtype.

### **2.2.1.1 Previous and ongoing clinical studies**

At the time of writing, RO7017773 has been investigated in three healthy adult participant studies, two ongoing studies; an Entry-into-Human study (BP40091) with single ascending doses (SAD) and multiple ascending doses (MAD), Drug-Drug interaction (DDI) study with itraconazole and one completed positron emission tomography (PET) study (BP40257). A summary is provided below but further information on the SAD and PET studies are provided in the IB.

[REDACTED]

[REDACTED]

[REDACTED]

[REDACTED]

[REDACTED]

[REDACTED]

[REDACTED]

[REDACTED]

**RO7017773—F. Hoffmann-La Roche Ltd**  
28/Protocol BP40950, Version 2

[REDACTED]

[REDACTED]

Further information regarding pre-clinical drug metabolism, pharmacokinetics, safety and toxicology, and results from clinical studies with RO7017773 can be found in the Investigator's Brochure (IB).

[REDACTED]

[REDACTED]

[REDACTED]

[REDACTED]

[REDACTED]

[REDACTED]

[REDACTED]

### **3. OBJECTIVES AND ENDPOINTS**

The objectives and corresponding endpoints are provided in [Table 6](#).

**Table 6 Objectives and Endpoints**

	Objectives	Endpoints
Primary		
PART 1	
 
• To assess the relative bioavailability of Phase II tablet formulation compared to Phase I capsule formulation of RO7017773 swallowed whole under fasting conditions following single oral dose administration.
 
	
 
• RO7017773 concentrations and RO7017773 pharmacokinetics (PK) parameters
 

PART 2	
 
• To assess the taste masking of RO7017773 Phase II tablet formulation containing sweetener and flavor dispersed in water and the RO7017773 Phase II tablet formulation without sweetener and flavor dispersed in apple juice.
 
	
 
• Taste questionnaire
 

Secondary		
PART 1	
 
• To assess the PK of RO7017773 Phase II tablet formulation dispersed in water or swallowed whole.
 
• To assess the effect of a high-fat meal on the PK (PK) of a single oral dose of RO7017773 Phase II tablet formulation.
 
• To assess the taste of RO7017773 Phase II tablet formulation without sweetener and flavor dispersed in water.
 
	
 
• RO7017773 concentrations and RO7017773 PK parameters
 
• RO7017773 concentrations and RO7017773 PK parameters
 
• Taste questionnaire
 

PART 2	
 
• To assess the PK of RO7017773 Phase II tablet formulation containing sweetener and flavor dispersed in water and the RO7017773 Phase II tablet formulation without sweetener and flavor dispersed in apple juice.
 
	
 
• RO7017773 concentrations and RO7017773 PK parameters
 

ALL PARTS	
 
• To evaluate the safety and tolerability of single oral doses of different RO7017773 formulations in healthy participants.
 
	
 
• Incidence and severity of AEs.
 
• Changes in vital signs, physical findings, ECG parameters, and clinical laboratory results during and following RO7017773 administration
 

Tertiary/Exploratory		
ALL PARTS	
 
• To screen for the presence of RO7017773-derived metabolites.
 
• To assess the relative abundance and PK parameters of any metabolite as appropriate
 
	
 
• PK concentrations of RO7017773-derived metabolites, if appropriate.
 
• PK concentrations of RO7017773-derived metabolites, if appropriate.
 

## 4. **STUDY DESIGN**

### 4.1 **OVERALL DESIGN**

An overview of the study design is provided in [Section 1.2](#).

This is a single-center, randomized, single-dose, open-label, crossover study in healthy participants. The study consists of two parts. Part 1 will enroll 16 participants to assess the performance of the Phase II tablet formulation as compared to the Phase I capsule formulation and a further eight participants will assess the taste of RO7017773 in Part 2. See [Section 4.1.1](#) for the details of the dosing regimen in both parts.

The primary objective of Part 1 is to determine the relative bioavailability of the two RO7017773 formulations administered under fasting conditions; Phase I capsule formulation (Treatment A) and Phase II tablet formulation (Treatment B). The food effect of the RO7017773 Phase II tablet formulation will be explored in Part 1 of the study, in order to understand whether the pharmacokinetic properties of the Phase II tablet formulation of RO7017773 are impacted when administered under fasting or fed conditions (Treatment C). As per the Food and Drug Administration (FDA) Guidance for Industry: Food Effect Bioavailability and Fed Bioequivalence Studies, the test meal provided will be a high-fat and high-calorie meal ([FDA 2002](#)). The PK of the Phase II tablet formulation dispersed in water (Treatment D), will be compared with the Phase II tablet formulation swallowed in fasted state. Furthermore, a taste assessment of the Phase II tablet formulation dispersed in water will be conducted (Treatment D).

All participants in Part 1 will receive all four treatments in a randomized, crossover design. Each treatment will be given as a single dose on Day 1 of each Treatment Period.

In Part 2, the taste of the Phase II tablet containing flavor and sweetener dispersed in water (Treatment A) will be investigated to understand how the taste is perceived. Additionally, the taste of the Phase II tablet without sweetener/flavor dispersed in apple juice will be assessed (Treatment B). A maximum of eight participants will be enrolled in Part 2 of the study. All participants in Part 2 will receive both treatments in a randomized, crossover design.

The washout period between each dose in both study parts will be at least 7 to 10 days. Participants will have to stay in the clinic from the day before each dosing (Day -1) to Day 3 after dosing for each Treatment Period. Ambulatory visits on Day 4 and Day 5 after each dosing are planned for PK sampling and safety monitoring. Approximately 7 to 14 days after their last dose participants will return to the clinic for a final follow-up visit.

